# **18.0** Confidentiality

# A. Confidentiality of Study Data

Describe the local procedures for maintenance of confidentiality of study data and any records that will be reviewed for data collection.

18.1 A. Where and how will all data and records be stored? Include information about: password protection, encryption, physical controls, authorization of access, and separation of identifiers and data, as applicable. Include physical (e.g. paper) **and** electronic files.

#### Response:

The signed consent documents and screening form with patient ID sticker will be placed in locked data boxes in the ED and PICU. The study coordinator will collect these documents on a daily basis, and store them in a locked file cabinet in Conventus building, Room 5154, [name].

All study associated data will be collected by [name] and co-PI, [name] at their offices located in the PICU attending and ED fellow offices. Both offices, Room 5281 and 5238, are located on the 5th floor in Conventus building. They will collect data by logging in password protected Kaleida electronic Powerchart system.

Study data will be entered into a password protected UB online secure database, REDcap by Drs. [name] or [name]. If data is collected at any time using paper forms, these forms will be discarded into a HIPAA bin once entered into REDcap. PHI including ED admission date, PICU admission and discharge date, and hospital discharge date will be collected in data form. Each subject's data will be identified using an assigned study ID. The study ID number will be used to label the subject's data forms and will also be the code key to link the subjects' identities and their data. The PI and co-PI will be fully responsible to protect the confidentiality of the data in the process of collecting data.

Subject's study ID number, randomization group, medical record number Record ID and enrollment date will be documented on a subject enrollment log, the Record ID is generated by REDCap when a subject data is entered in the database. The subject enrollment log will be saved on a secure online drive in the study coordinator, PI and Co-PI ([name])'s password-protected computers.

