#### Response:

This is a single center, double blinded, randomized controlled trial with two treatment arms to be performed at a single tertiary care children's hospital. Patients will be randomized within 2 hours of initiation of care to receive DKA management using intravenous fluids containing primarily normal saline or lactated ringers. All other aspects of DKA management will be the same in each arm, per the institution protocol.

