# **10.0 Procedures Involved**

10.1 Provide a description of **all research procedures or activities** being performed and when they are performed once a subject is screened and determined to be eligible. Provide as much detail as possible.

*NOTE:* This should serve as a blueprint for your study and include enough detail so that another investigator could pick up your protocol and replicate the research. For studies that have multiple or complex visits or procedures, consider the addition of a schedule of events table in in your response.

Upon consenting, a copy of the signed informed consent document with the subject name and medical record number will be sent to our inpatient pharmacy by an ED research assistant if the subject is enrolled in the ED. If a subject is enrolled in the PICU, the signed consent will be faxed to the inpatient's pharmacy. Meanwhile, the study protocol will be placed using an electronic order set containing the study DKA management protocol that is identical to the routine management of DKA with the exception of the fluid content per arm. Please refer to study protocol schematic shown in supplement 1.

After receiving the copy of the consent, patients will be randomly assigned a treatment arm (group A or B) and a study ID by the pharmacy following a randomization table generated by a statistician. Each group correlates with a treatment arm assignment visible on a randomization table available only to the inpatient pharmacy personnel. Pharmacy personnel will then provide the appropriate content to the intravenous fluids with a generic label "DKA study fluids with dextrose" and "DKA study fluids without dextrose." The fluids look identical as the bags will be labeled with standardized labelling as "DKA Study fluid with dextrose" or "DKA study fluid without dextrose." The study ID will also be labeled on the bags and typed into the electronic orders by pharmacy. The bags will be properly covered by the labels to ensure complete blinding of the subject and the medical treatment team. The intravenous fluids will be transported to the patients per the regular system used in the ER and PICU.

We anticipate that the eligible patients will be consented within 2 hours of arrival to the PICU or after the first provider makes contact in the ED and shortly thereafter started on continuous infusions of intravenous fluids and insulin per the study protocol.

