#### Response:

Univariate analysis will be used to determine if the subjects in each treatment arm differ at baseline through t-test or Wilcoxon Rank Sum testing for continuous data and Chi-square testing for categorical data. Any differences will be controlled for in the analysis of the primary outcome (length of acidosis) using linear regression. All outcomes will be correlated with the overall chloride load given via intravenous fluids during DKA management. All analyses will be performed using IBM SPSS software, version 25 (Chicago, IL) and SAS (SAS Institute Inc., Cary, NC) with significance set at p<0.05.

17.2 If applicable, provide a power analysis.

*NOTE:* This may not apply to certain types of studies, including chart/records reviews, survey studies, or observational studies. This question is asked to elicit

whether the investigator has an adequate sample size to achieve the study objectives and justify a conclusion.

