#### 18.5 A. How will the data be transported?

Response:

Data will be entered in password protected electronic database REDCap. The study coordinator will manually collect informed consent and screening forms from ED and PICU. In addition, the coordinator will send the subject enrollment log to the PI and co-PI via secure email system.

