#### Response:

Please refer to section 18 for protecting the confidentiality about study data. In summary, signed informed consent and patient screening form will be stored in locked study boxes in the ED and PICU and collected daily by the study coordinator, and then stored in locked file cabinet in research document room in the Conventus building. Data will be collected by PI and co-PIs (Drs. [name] and [name]) in their offices and entered directly in password protected online secure database RedCap. Subject enrollment log will be sent by the coordinator to the PI and co-PI via secure email system and stored in password protected UPA online secure drive.

21.3 If applicable, indicate **which procedures** may have risks to the subjects that are currently unforeseeable.

Response:

None

21. 4 If applicable, indicate which research procedures may have risks to an embryo or fetus should the subject be or become pregnant.

Response:

None

21.5 If applicable, describe risks to others who are not subjects.

Response:

None

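### The enrollment log gives the PI, co-PI and coordinator each subject's coded randomization group, for no stated purpose, in a trial declared double blind

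*Combined protocol and SAP*

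**What the plan says.** - Design (section 4.1): "This is a single center, double blinded, randomized controlled trial with two treatment arms".
- Assignment (section 10.1): "patients will be randomly assigned a treatment arm (group A or B) and a study ID by the pharmacy". The arm behind each group is "visible on a randomization table available only to the inpatient pharmacy personnel". Section 31.2 likewise limits the table to pharmacy.
- Who is masked (sections 10.1 and 31.2): the subject, the medical treatment team, bedside staff and treating physicians.
- Enrollment log (section 18.1 A): each subject's "study ID number, randomization group, medical record number Record ID and enrollment date will be documented on a subject enrollment log". The log is stored for the coordinator, the PI and the co-PI. The same section says that the study ID "will also be the code key to link the subjects' identities and their data".
- Circulation (section 18.5 A): "the coordinator will send the subject enrollment log to the PI and co-PI via secure email system". Section 21.2 repeats this.
- Roles: under section 21.2, "Data will be collected by PI and co-PIs". Under 17.3 the PI reviews all data for outliers. Under 19.2 the investigator judges whether changes and events matter and whether they are tied to study procedures. Under 26.4 the PI or coordinator checks on the patient each day.

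No section says when the group is entered on the log, delays the entry until the data are final, or gives a reason for it.

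**The concern.** Sections 10.1 and 31.2 confine the arm table to pharmacy. Section 18.1 A then places one half of the decoding information, each named subject's group, with people outside pharmacy who run the trial day to day. Their masking then depends only on nobody learning what a single letter stands for. If that happened, later judgments about adverse events and data queries would be made by people able to infer the arm of every logged subject. In a double-blind trial, the holders of such a list would be expected to need it, and here no need is stated.

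**Working it through.** The plan gives no figure to reproduce. The check sets the sections side by side.

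1. What the log reveals. Section 18.1 A says only that the randomization group is recorded. Section 10.1 defines the group as A or B and keeps its meaning in pharmacy. Read together, the log shows a letter beside a medical record number. It does not show the fluid.

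2. What one disclosure would reveal. Finding a subject's fluid takes two items: the subject's letter and the meaning of the letter. With two arms and one fixed letter each, learning that one subject with letter A receives a given fluid also settles letter B by elimination.

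| State of the log | Subjects decoded if one subject's fluid becomes known |
|---|---|
| Group recorded as a fixed A/B letter | every subject logged, at most the planned 104 (section 5.1) |
| Group not recorded | 1 |

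This is conditional on a disclosure. It is not a probability that one occurs, and no section describes an event that would cause one.

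3. Who would be affected.

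| Function | Role named | Section |
|---|---|---|
| Holds or receives the log | coordinator, PI, co-PI | 18.1 A, 18.5 A, 21.2 |
| Daily contact with the subject | PI or coordinator | 26.4 |
| Collects study data | PI and co-PIs | 21.2 |
| Reviews data for outliers | PI | 17.3 |
| Judges clinical importance and association with study procedures | the investigator | 19.2 |

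The roles that hold the log therefore overlap with the roles that exercise judgment.

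4. Whether the entry is needed. The log's evident task is to link a person to a data record. The study ID, the medical record number and the REDCap Record ID do that without the group. Analysis by arm does need the group, but section 18.3 A assigns analysis to a statistician working on de-identified data, who does not need this log.

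5. Where knowledge of the arm could act. The primary outcome uses laboratory thresholds (section 2.1) on a test schedule common to both arms (section 10.1), which leaves little room for judgment. Decisions on events (19.2) and on queries (17.3) leave more.

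**The case against.** The strongest reply is that nothing declared has been broken. The plan names those it masks, and a coded log unmasks none of them. The key stays in pharmacy, and no leak is described. That stands: this is avoidable exposure, not a contradiction or an unblinding.

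A second reply concerns consequences. The only safety test planned (section 19.6) compares observed rates with previously reported rates, not one arm with the other. Biased event judgment would therefore not enter a planned between-arm safety comparison. This also stands. What remains exposed is the individual decision on whether an event is reportable, together with data queries.

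Three stronger readings are tempting, and the documents do not support them.

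- A reader might infer that the investigators are unblinded. The letter alone does not identify the fluid.
- A reader might infer that the six-monthly analyses would expose the code. Section 19.5 speaks of aggregate data, and neither it nor 19.6 says that these analyses are by group.
- A reader might infer that log holders could foresee the next assignment and steer recruitment. Assignment follows signed consent, and no predictable sequence is given.

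None of these replies supplies a reason for recording the group on the log.

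**Conclusion.** The point holds as a low-cost improvement. Section 18.1 A gives the coordinator, PI and co-PI a per-subject arm code that no section says they need. It thereby makes their masking depend on a single fact that could decode the whole log. No actual unblinding is claimed, and no stated masking is breached.

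The effect, if the code became known, is that one disclosure would reach every logged subject instead of one. The likely consequence for the primary outcome is small. A reader might also infer an effect on length of stay, but that would require a log holder to be treating the subject, which the documents do not establish.

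The conclusion rests on two assumptions. The first is that the log entry is the fixed A/B letter of section 10.1; if it were unique to each subject, one disclosure would identify only that subject. The second is that the entry is made during the trial, since no section defers it.

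**What to change.** In section 18.1 A, strike the randomization group from the contents of the enrollment log and leave the other fields as they are. State in the same place, or in 10.1, that the link between study ID and group stays in pharmacy and is released only to the statistician, when an analysis by group needs it. That list should carry study ID and group only, which fits the limit in section 18.3 A on the statistician's access to identifiers.

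The cost is a short wording change and one list transfer from pharmacy to the statistician for each analysis by group. It adds no patients, tests or visits. If the investigators have a reason to keep the group on the log, the alternative is to state that reason and who may see the entry.

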#### 18.2 A. How long will the data be stored?

#### Response:

The electronic database saved in REDCap will be stored online indefinitely. Enrollment logs will be stored for three years after study is closed by IRB, then it will be deleted from the online secure drive. Signed informed consent and screening forms will be stored in locked file cabinet for three years after study is closed.

#### 18.3 A. Who will have access to the data?

#### Response:

The PI, co-PIs will have access to the data. The statistician will have access to the de-identified data for data analysis purposes, but will not have access to any PHI. The study coordinator will have access to the signed consent documents and the screening forms.

18.4 A. Who is responsible for receipt or transmission of the data?

#### Response:

The study coordinator will be responsible for transmission of the signed consent, screening form and the subject enrollment log.

#### 18.5 A. How will the data be transported?

Response:

Data will be entered in password protected electronic database REDCap. The study coordinator will manually collect informed consent and screening forms from ED and PICU. In addition, the coordinator will send the subject enrollment log to the PI and co-PI via secure email system.

# **B.** Confidentiality of Study Specimens

*Describe the local procedures for maintenance of confidentiality of study specimens.* 

■ N/A: No specimens will be collected or analyzed in this research. (*Skip to Section 19.0*)

18.6 B. Where and how will all specimens be stored? Include information about: physical controls, authorization of access, and labeling of specimens, as applicable.

Response:

18.7 B. How long will the specimens be stored?

Response:

18.8 B. Who will have access to the specimens?

Response:

18.9 B. Who is responsible for receipt or transmission of the specimens?

Response:

18.10 B. How will the specimens be transported?

Response:

# **19.0** Provisions to Monitor the Data to Ensure the Safety of Subjects

□ N/A: This study is not enrolling subjects, or is limited to records review procedures only. This section does not apply.

*NOTE:* Minimal risk studies may be required to monitor subject safety if the research procedures include procedures that present unique risks to subjects that require monitoring. Some examples include: exercising to exertion, or instruments that elicit suicidality or substance abuse behavior. In such cases, N/A is not an acceptable response.

19.1 Describe the plan to periodically evaluate the data collected regarding both harms and benefits to determine whether subjects remain safe.

#### Response:

Subjects enrolled in this study will receive intravenous fluid containing normal saline or lactated ringer's; both fluids are considered standard of care in the treatment of DKA. There is no other intervention for this study, we believe this study does not involve more than minimum risk to the participants. However, interim outcome analysis will be performed every 6 months to identify any problems that may associate with the study.

19.2 Describe what data are reviewed, including safety data, untoward events, and efficacy data.

In the interim analysis, patient outcomes will be reviewed as will any adverse events. An adverse event will be defined as any clinically important untoward medical occurrence in a child enrolled in this study different from what is expected in the clinical course of a child with DKA.

The investigator will evaluate any changes in laboratory values and physical signs and will determine if the change is clinically important and different from what is expected in the clinical course patients with DKA. Expected events for DKA are untoward clinical occurrences that are perceived by the investigator to occur with reasonable frequency in the day-to-day care of patients with DKA treated in an intensive care unit. Examples of expected events that may occur during treatment of DKA include cerebral edema, thrombotic events, acute kidney injury, hypokalemia, hypomagnesemia, hypophosphatemia, hypernatremia, hyponatremia, hyperchloremia, hyperglycemia and hypoglycemia.

Expected events will be evaluated monthly by the investigators and will not be considered reportable unless the event is considered by the investigator to be associated with the study procedures such as unexpectedly severe or more frequent than usually seen in the treatment of DKA. Organ failures related to DKA or an underlying condition will not be reported as adverse events. These will be captured in the data collection form but are routine occurrences during the treatment and recovery phase of DKA.

19.3 Describe the frequency of safety data collection.

Response:

As there is minimal risk related to this study, no regular safety data will be collected.

19.4 Describe who will review the safety data.

Response:

As there is minimal risk related to this study, no regular safety data will be collected nor will need review.

19.5 Describe the frequency or periodicity of review of cumulative safety data.

Response:

The aggregate study data will be analyzed every 6 months. The frequency of all expected complications from DKA will be analyzed at that time.

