# 3.0 Background

3.1 Provide the scientific or scholarly background, rationale, and significance of the research based on the existing literature and how it will contribute to existing knowledge. Describe any gaps in current knowledge. Include relevant preliminary findings or prior research by the investigator.

Response:

Diabetic Ketoacidosis occurs in approximately 30% of children with new onset type 1 diabetes mellitus (T1DM) and 5-10% of newly diagnosed children with type 2 diabetes [1]. DKA is a decompensated metabolic state resulting from insulin deficiency. DKA is characterized by acidosis, ketonemia, ketonuria, and hyperglycemia. Mortality from DKA in the United States is about 0.15%. Morbidity related to DKA is caused by shock, intestinal ischemia, cardiac arrhythmias, thrombosis, and cerebral edema [2, 3]. Clinically significant cerebral edema occurs in just 0.3-1% of all DKA, but results in 55-87% of all deaths related to DKA. The exact etiology of cerebral edema in DKA remains unclear, but it is consistently associated with osmotic shifts, hypoventilation, cerebral hypoperfusion, and administration of bicarbonate. With the intent to prevent shock, ischemia, and the thrombotic state, providers tend to administer large amounts of intravenous fluids in the form of 0.9% saline, also called normal saline, to patients in the initial treatment of DKA. Aggressive fluid administration has been shown to increase the risk of cerebral edema and does not reverse the primary metabolic deficiency driving the acidosis [4, 5].

During the treatment and recovery phases of DKA, the continued use of aggressive amounts of NS may be the mechanism by which patients develop a hyperchloremic metabolic acidosis (HMA) as NS contains a higher chloride concentration than serum. The detrimental clinical consequences of a high chloride load from intravenous fluids have been demonstrated in patients after trauma, in acute kidney injury, and in certain shock states [6, 7]. During HMA in

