After admission to the PICU, DKA fluid management uses a two-bag system to maintain glucose levels between 100 and 300 mg/dL. Once the patient's glucose concentration falls below 300 mg/dL, the intravenous fluids containing dextrose are started and the fluids without dextrose are titrated downward. In addition to containing necessary electrolytes, the study intravenous fluids will contain either lactated ringer's or normal saline based on the assigned treatment arm.

Study fluid management of the two-bag system will follow the same guidelines for rate of fluid delivery and amount of dextrose used currently in the routine management of patients in DKA. Bedside healthcare personnel will treat all study subjects identically regardless of treatment arm. To provide blinding to all bedside staff, intravenous fluid bags will be labelled as "DKA study fluid with dextrose" or "DKA study fluid without dextrose." The fluid bags will be covered with an opaque black bag to mask any visible description of the fluid content.

Fluids will be adjusted using the study protocol as outlined here:

Serum Glucose	DKA study fluids without dextrose	DKA study fluids with dextrose	
>300mg/dL	100% of the hourly rate	0%	

200-300 mg/dL	50% of the hourly rate	50% of the hourly rate	
<200 mg/dL	0%	100% of the hourly rate	

Study participants will not receive any additional laboratory tests other than those that are already involved in standard DKA management. Currently, routine DKA management involves hourly finger-stick or laboratory glucose levels, every 2-hour serum electrolytes and blood gases, every 6-hour serum beta-hydroxybutyrate levels, and urine ketones with every void. This will be the same for all study participants on both treatment arms.

The study fluids will be used until the acute management of DKA using the continuous insulin infusion and two-bag fluid system is stopped. This will occur when the venous pH is equal to or greater than 7.30, the serum bicarbonate level is equal to or greater than 15 mmol/L and serum ketone levels are less than 1mmol/L.

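### Expected DKA complications stay out of adverse-event reporting by default, and no comparison of them between the randomized arms is planned

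*Combined protocol and SAP*

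**What the plan says.** Section 19.2 defines an adverse event as a clinically important untoward occurrence "different from what is expected in the clinical course of a child with DKA". It then lists what is expected: "Examples of expected events that may occur during treatment of DKA include cerebral edema, thrombotic events, acute kidney injury", followed by eight electrolyte and glucose disturbances that include hyperchloremia, which makes 11 named events.

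Three rules follow in the same section:

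- Expected events are looked at monthly by the investigators, but they "will not be considered reportable unless the event is considered by the investigator to be associated with the study procedures". The sentence goes on "such as unexpectedly severe or more frequent than usually seen in the treatment of DKA", so severity and frequency are part of the exception.
- For organ failure the rule is flat: "Organ failures related to DKA or an underlying condition will not be reported as adverse events". No exception is attached to it.
- Organ failures are nevertheless entered on the data collection form.

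Section 19.5 has the aggregate data analysed every 6 months, including the frequency of all expected complications. Section 19.6 tests the observed rates, one-sided, against previously reported rates, and gives no such rates. Sections 19.3 and 19.4 say that safety data will not be regularly collected and need no review. Section 19.7 names no event that would suspend the trial.

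**The concern.** Some of the events filtered out are ones that the protocol itself connects with the fluids under test. Section 3.1 attributes hyperchloremic acidosis to saline, and section 22.1 hopes to reduce it. Section 3.1 also states: "The detrimental clinical consequences of a high chloride load from intravenous fluids have been demonstrated in patients after trauma, in acute kidney injury". Hyperchloremia is thus close to the effect that the trial is designed to find and, by default, is not an adverse event.

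Both fluids are routine care, and one child's kidney injury cannot be assigned to a fluid rather than to DKA. Case-by-case attribution therefore says little about a fluid effect. What could show one is a count by randomized arm, and the plan has none for these events. At stake is whether an excess of complications on one fluid would be visible in a trial that has a concurrent randomized control but compares its complications with outside figures.

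**Working it through.** **No plan figure to reproduce.** The point concerns a reporting rule and the choice of comparator. The arithmetic below shows what that comparator can and cannot see.

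**Inputs.** 104 children, 52 per arm (section 5.1). Cerebral edema rate from section 3.1: "Clinically significant cerebral edema occurs in just 0.3-1% of all DKA, but results in 55-87% of all deaths related to DKA". One-sided comparison with previously reported rates (section 19.6). Section 19.6 states no significance level, so 0.05 is assumed from section 17.1. Background rates of 5%, 10% and 20% are assumptions that stand for commoner complications. An exact binomial test is used in place of the planned t-test, as a single look at full enrolment.

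**Step 1: cerebral edema.** Expected cases are 104 × 0.003 = 0.31 to 104 × 0.01 = 1.04, or 0.16 to 0.52 per arm. The chance of at least one case is 1 − (1 − p)^104, which is 27% at 0.3% and 65% at 1%.

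**Step 2: dilution.** If one of two equal arms has twice the usual rate, the pooled ratio is (1 + 2)/2 = 1.5.

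**Step 3: power when one arm doubles and the benchmark is exactly right.** The between-arm figures use the normal approximation, which is rough at the two lowest rates.

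| Usual rate | Pooled rate | Cases in 104 needed to signal | Pooled v benchmark, one-sided | Between arms, one-sided | Between arms, two-sided |
|---|---|---|---|---|---|
| 0.3% | 0.45% | 2 | 8% | 8% | 4% |
| 1% | 1.5% | 4 | 7% | 11% | 6% |
| 5% | 7.5% | 10 | 25% | 25% | 16% |
| 10% | 15% | 17 | 39% | 41% | 30% |
| 20% | 30% | 29 | 72% | 72% | 61% |

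With a correct benchmark, the pooled check is about as powerful as a one-sided between-arm test. The weakness lies in its dependence on the benchmark and its blindness to arm, which the next two steps show.

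**Step 4: dependence on the benchmark.** The protocol's own range for cerebral edema spans a factor of 1/0.3 = 3.3 and refers to all DKA, whereas this trial enrols children who need intensive care. Moving from one end of the range to the other shifts the signal from 2 cases to 4. A true rate of 0.3% that doubles in one arm pools to 0.45%, still below half of a 1% benchmark.

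**Step 5: masking.** Assume arms at 10% and 30% and a published rate of 20%. The pooled rate is (10 + 30)/2 = 20%, equal to the benchmark. The planned check signals with probability 2.9%, whereas a two-sided between-arm test at 0.05 has 73% power.

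**Step 6: the text side by side.** Section 19.2 has a monthly evaluation, 19.5 a 6-monthly analysis and 19.6 a test. Sections 19.3 and 19.4 say that there is nothing to collect regularly or to review. Both cannot be followed.

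**The case against.** The strongest reply is that these events lose a label, not their place in the data. They are evaluated monthly, analysed every 6 months and tested against published rates, and organ failures go on the form. Unexpected events stay reportable, and so do expected ones that are unusually severe or frequent. This stands. A reader might infer that the trial will show almost no adverse events whatever the fluids do, or that a case of cerebral edema would prompt no review. The documents do not support either.

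A reader might also suppose that the attribution is made by a blinded investigator. Section 10.1 masks bedside staff ("The fluid bags will be covered with an opaque black bag to mask any visible description of the fluid content") and states blinding for the subject and the treating team. Section 18.1 A, however, puts the randomization group on a log held by the coordinator, the PI and a co-PI, without saying whether that means the A/B code or the fluid. Investigator blinding is not established, and the point does not rely on it.

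The background should not be stretched. Section 3.1 ties cerebral edema to aggressive fluid administration, which is volume, and rate guidelines are the same in both arms. It does not say that saline causes kidney injury in DKA. Nor does the protocol plan any claim that the fluids are equally safe.

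Section 17.1 relates all outcomes to chloride load, but the outcomes in section 10.2 are length of stay and resolution of acidosis, so complications are not clearly covered. In section 19.5, aggregate may mean cumulative rather than pooled across arms. Even so, nothing in section 19 mentions an arm, and the only stated comparator is external.

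Finally, by-arm counts will not detect a doubling of cerebral edema: power is about 4–6%. That limits what a test can do. It does not argue against showing the counts.

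**Conclusion.** The point holds in a limited form. By default, the 11 named complications fall outside adverse-event reporting, and DKA-related organ failure is excluded without exception. They are still captured and reviewed, but against previously reported rates that are not specified, and no section compares them between the arms. An excess on one fluid is diluted (twice the usual rate reads as 1.5 times), is not attributed to an arm, and can be hidden if the benchmark is too high or the other arm runs low. The 2.9% against 73% contrast illustrates this under assumed rates of 10%, 30% and 20%; it is not a forecast. If the benchmark were exactly right, the pooled check would lose little power, so the case for change rests on the uncertainty of the benchmark and on the randomized control being available. Separately, sections 19.3 and 19.4 contradict 19.2, 19.5 and 19.6.

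**What to change.** In sections 19.2, 19.5 and 19.6:

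- Make the listed complications, organ failure and death prespecified safety outcomes. Record every occurrence after randomization whatever its presumed cause or expectedness, and keep the attribution judgment as a recorded field only.
- Define laboratory events by prespecified cut-offs that allow for values already abnormal at entry, for example new or worsening after randomization. Section 6.1 requires glucose above 200 mg/dl, so a simple count of hyperglycemia could include almost every child.
- Tabulate counts and risk differences with confidence intervals by randomized arm, at the end of the trial and in each 6-monthly review, in place of or alongside the comparison with published rates. Use coded arms in the interim tables. A difference in hyperchloremia could reveal the code, so those tables are best kept from the treating team.
- If the historical comparison stays, state the rates and their source.
- Confirm that the forms record cerebral edema, thrombosis, magnesium and phosphate. Section 10.2 does not name them, and the forms are not part of the document.
- Reconcile sections 19.3 and 19.4 with 19.2, 19.5 and 19.6.

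The cost is protocol wording, a longer safety table and possibly a few form fields. Rare events such as cerebral edema will be descriptive only.
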